11.14 Inclusion of Women and Minorities

This study should attract a diverse study population. If difficulty is encountered in recruiting an adequate number of women and/or minorities, the difficulties involved in recruitment will be discussed and plans implemented to increase representation by all sex and racial/ethnic groups.

11.15 Description of Plans to Conduct Valid Analyses of Study Results by Gender and Race/Ethnicity

The association between specific demographic characteristics and outcome will be studied. The demographic characteristics of potential importance include: age, gender, race, and ethnicity.

11.16 Regulatory Files

The regulatory files should contain all required regulatory documents, study-specific documents, and all important communications. Regulatory files will be checked for regulatory document compliance prior to study initiation, throughout the study, as well as at study closure.

11.17 Records Retention and Requirements

Research records for all study participants (e.g., case report forms, source documents, signed consent forms, and regulatory files) are to be maintained by the investigator in a secure location for a minimum of 3 years after the study is completed and closed. These records are also to be maintained in compliance with local IRB, State and Federal requirements, whichever is longest. The sponsor must be notified in writing and acknowledgment must be received prior to the destruction or relocation of research records.

11.18 Audits

The Sponsor has an obligation to ensure that this trial is conducted according to good research practice guidelines and may perform quality assurance audits for protocol compliance. The Investigator; the National Institute on Drug Abuse (the study sponsor); NIDA's contracted agents, monitors or auditors; and other agencies such as the Department of Health and Human Services (HHS), the Office for Human Research Protection (OHRP) and the sites' Institutional Review Board may inspect research records for verification of data, compliance with federal guidelines on human participant research, and to assess participant safety.

11.19 Reporting to Sponsor

The Principal Investigator agrees to submit accurate, complete, legible and timely reports to the Sponsor, as required. These include, but are not limited to, reports of any changes that significantly affect the conduct or outcome of the trial or increase risk to study participants. Adverse Event reporting and Serious Adverse Event reporting will occur as previously described. At the completion of the trial, the PI will provide a final report to the Sponsor.

11.20 Study Documentation

Study documentation includes all case report forms, data correction forms, workbooks, source documents, monitoring logs and appointment schedules, sponsor-investigator correspondence, and signed protocol and amendments, Ethics Review Committee or Institutional Review Committee correspondence and approved current and previous consent forms and signed participant consent forms.

Source documents include all recordings of observations or notations of clinical activities and all reports and records necessary for the evaluation and reconstruction of the clinical research study. The original recording of an observation should be retained as the source document.

11.21 Protocol Deviations, Violations, and Reporting and Management

Any departure from procedures and requirements outlined in the protocol will be classified as either a protocol deviation or protocol violation. The difference between a protocol deviation and violation has to do with the seriousness of the event and the corrective action required. A protocol deviation is considered an action (or inaction) that by itself is not likely to affect the scientific soundness of the investigation or seriously affect the safety, rights, or welfare of a study participant. Protocol violations are departures that may compromise the participant safety, participant rights, inclusion/exclusion criteria or the integrity of study data and could be cause for corrective actions if not rectified or prevented from re-occurrence. Protocol violations will be monitored for (1) significance, (2) frequency, and (3) impact on the study objectives, to ensure that performance does not compromise the integrity of the trial.

Additionally, the study team is responsible for reporting Protocol Violations to the IRB as required.

11.22 Safety Monitoring

11.22.1 Adverse Events (AEs)

In accordance with FDA reporting requirements, all AEs occurring during the course of the clinical trial will be collected, documented, and reported by the Principal Investigator or sub-investigators according to the specific instructions detailed in this section of the protocol and Appendix A. The occurrence of AEs will be assessed at each study visit starting at the time that informed consent is signed through the post-medication assessment, and study staff will follow-up on the status of any AEs that remain at the post-medication assessment.

An AE is defined as any reaction, side effect, or untoward event that occurs during the course of the clinical trial, whether or not the event is considered investigational product-related or clinically significant. For this study, AEs will include events reported by the participant, as well as clinically significant abnormal findings on physical examination or laboratory evaluation. A new illness, symptom, sign or clinically significant clinical laboratory abnormality or worsening of a pre-existing condition or abnormality is considered an AE. Stable chronic conditions, such as arthritis, which are present prior to clinical trial entry and do not worsen are not considered AEs. All AEs must be recorded on the AE Form. The AE Form is also used to record follow-up information for unresolved events reported on previous visits.

Each week, a study physician or investigator must review the AE Form completed for the previous week for any events that were reported as continuing. All AEs, including clinically significant abnormal findings on laboratory evaluations, regardless of severity, will be followed by study investigators until satisfactory resolution.

A Medical Clinician will review or provide consultation for each serious event as needed. These reviews will include an assessment of the severity and causality to the study drug or study procedures. The Medical Clinician will also provide advice for decisions to exclude, refer, or withdraw participants as required. The medical monitor will determine which safety events require expedited reporting to the IRBs, NIDA, the DSMB, and other regulatory authorities as appropriate.

This will include all suspected adverse reactions that are serious and unexpected. The study staff will be trained to monitor for and report adverse events and serious events.

The BCMDC has established practices for managing medical and psychiatric emergencies, and the study staff will continue to utilize these procedures. Study medical clinicians will be responsible for monitoring participants for possible clinical deterioration or other problems, and for implementing appropriate courses of action.

11.22.2 Definitions of Adverse Events and Serious Adverse Events

Full definitions of adverse events and serious adverse events, their identification, characterization regarding severity and relationship to therapy and processing are described in Appendix A.

11.22.3 Reportable Adverse Events and Serious Adverse Events

Reporting of AEs and SAEs is described in Appendix A. The study investigators in this study have the responsibility of promptly reporting all SAEs to NIDA.

Adverse Events

For the purpose of this study, the following AE will not require reporting in the data system but will be captured in the source documentation as medically indicated:

• Grade 1 (mild) unrelated adverse events

This would typically include mild physical events such as headache, cold, etc., that were considered not reasonably associated with the use of the study drug/intervention.

Other adverse events that are deemed moderate, severe or serious, regardless of the relationship to the study medications, will be captured and reported in the data system.

Serious Adverse Events

All SAEs will be documented in the source documentation as medically indicated and reported through the data system.

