2.4 Interventions

All participants will be scheduled for twice-monthly medical management and assessment appointments for the first three months of the 24-week post-release intervention phase, with monthly appointments for months 4-6. Eligible participants will be randomly assigned to treatment condition (VI, PNV, DE) in equal numbers. VI and PNV participants will undergo a naloxone challenge to ensure opioid abstinence at the time of Vivitrol induction. Those in the PNV condition will be provided with a PN who will facilitate attendance at outpatient treatment programs as well as assist with other needs. The DE group will not receive any medication but will be scheduled for assessments and education on drugs of abuse, maintaining abstinence, and methods for avoiding overdoses on the same schedule as the other two groups. The DE group will also be

provided with naloxone kits to be used in the event of overdose. All groups will also be provided with referrals to community-based substance abuse treatment programs.

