7.14 Blinding

This is an open-label, non-blinded trial.

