Sites are required to enter reportable AEs and SAEs in the EDC system. The AE form is used to capture reportable AEs (as defined in the protocol). Additional information may need to be gathered to evaluate serious adverse events and to complete the appropriate CRFs and the summary. This process may include obtaining hospital discharge reports, medical records, autopsy records or any other type records or information necessary to provide a complete and clear picture of the serious event and events preceding and following the event. If the SAE is not resolved or stable at the time of the initial report or if new information becomes available after the initial report, follow-up information must be submitted as soon as possible.

Reportable adverse events will be followed until resolution, stabilization or study end. Any serious adverse reactions will be followed until resolution or stabilization even beyond the end of the study.

Assessing Severity and Causality of Adverse Events

Appropriately qualified and trained medical personnel will conduct an initial assessment of seriousness, severity, and causality when eliciting participant reporting of adverse events. A study medical clinician will review reportable AEs for seriousness, severity, and causality on at least a weekly basis.

Guidelines for Assessing Severity

The severity of an adverse event refers to the intensity of the event.

Grade 1 Mild Transient or mild discomfort (< 48 hours), no or minimal medical intervention/therapy required, hospitalization not necessary (non-prescription or single-use prescription therapy may be employed to relieve symptoms, e.g., aspirin for simple headache, acetaminophen for post-surgical pain)

hospitalization possible.

Grade 3 Severe Marked limitation in activity, some assistance usually required; medical intervention/ therapy required hospitalization possible.

Guidelines for Determining Causality

The study medical clinician will use the following question when assessing causality of an adverse event to study drug/intervention where an affirmative answer designates the event as a suspected adverse reaction:

Is there a reasonable possibility that the study drug/intervention caused the event?

Monitoring Adverse Events

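### Mild adverse events reach the data system only if an unblinded clinician judges them related, so any comparison of Grade 1 events between a Vivitrol arm and the no-drug DE arm is biased

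*Combined protocol and SAP*

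**What the plan says.** Section 11.22.3 (Reportable Adverse Events and Serious Adverse Events) states that "the following AE will not require reporting in the data system but will be captured in the source documentation as medically indicated". The single item listed is "Grade 1 (mild) unrelated adverse events", with headache and colds given as typical examples. The same section keeps everything above mild: "Other adverse events that are deemed moderate, severe or serious, regardless of the relationship to the study medications" are entered in the data system.

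Appendix A follows this rule. Sites must enter reportable events and serious events in the electronic system, and "The AE form is used to capture reportable AEs (as defined in the protocol)". Relatedness is decided by a study medical clinician, who answers one yes/no question: "Is there a reasonable possibility that the study drug/intervention caused the event"

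Section 11.22.1 defines an adverse event without regard to causality and says "All AEs must be recorded on the AE Form".

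Three other places matter. Section 7.14 says "This is an open-label, non-blinded trial". Section 2.4 (Interventions) says "The DE group will not receive any medication". Section 10.4.2 puts adverse events under descriptive statistics and adds that between-group comparisons can be tested, with chi-square for binary measures. Nothing there limits such tests by grade or by arm.

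**The concern.** Whether a mild event appears in the analysis data depends on a causality judgement, and the person judging knows the arm. In DE there is no drug to blame, so a mild headache or bout of nausea will almost always be judged unrelated and need not be entered. In VI or PNV the same complaint can reasonably be attributed to Vivitrol, because section 7.5.1 lists nausea and vomiting among its common effects, and it is then entered. Equal occurrence can give unequal records.

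What is at stake is the mild part of the tolerability picture when a Vivitrol arm is set against DE. A reader of such a table could take a difference in recording for a drug effect, or misjudge the size of a real one. Section 10.3 says the results are meant to inform a larger multi-site trial, so a misleading mild-event profile could carry forward.

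**Working it through.** The documents give no mild-event rate and no attribution rate, so there is no planned figure to reproduce. The check has three parts.

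**1. The rules side by side**

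| Event | VI or PNV | DE |
|---|---|---|
| Grade 1, judged related | entered | entered, but rarely so judged |
| Grade 1, judged unrelated | need not be entered | need not be entered |
| Grade 2 or above, or serious | entered | entered |

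The written rule is the same in every arm. The difference comes from how often a mild event lands in the first row. If the true risk of a mild event is b and a share r is judged related, the recorded risk is b × r. A comparison with DE is fair only if r is equal in both arms.

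**2. An event with no drug effect**

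Inputs: 50 per arm (section 10.3); two-sided .05 (section 10.0); chi-square (section 10.4.2). Assumptions: b = 20% in both arms, and r = 0 in DE.

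With x recorded events in VI and none in DE, the uncorrected chi-square statistic is 100x / (100 − x).
- x = 3 gives 300/97 = 3.09, which does not reach 3.84.
- x = 4 gives 400/96 = 4.17, p = 0.041. The test therefore rejects from 4 events.
- Fisher's exact test gives p = 0.117 at x = 4, 0.056 at x = 5 and 0.027 at x = 6. It rejects from 6 events.

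The rejection probability is P(X ≥ 4) or P(X ≥ 6), where X is binomial with n = 50 and probability 0.20 × r.

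| r in VI | Recorded VI vs DE | Chi-square | Fisher |
|---|---|---|---|
| 10% | 2% vs 0% | 1.8% | about 0% |
| 25% | 5% vs 0% | 24% | 3.8% |
| 50% | 10% vs 0% | 75% | 38% |

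If every event is entered (20% vs 20%), the chi-square test rejects in 5.2% of trials.

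Two variations:
- At 40 per arm (the 120 evaluable participants in section 10.3 divided by three), Fisher's test gives 1.4% at r = 25% and 21% at r = 50%.
- With DE not fixed at zero (b = 40%, r = 25% in VI and 5% in DE), recorded risks are 10% vs 2%. Chi-square rejects in 38% of trials and Fisher's test in 19%.

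**3. An event with a real drug effect**

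Take the nausea figures in section 7.5.1 (33% Vivitrol, 11% placebo) as assumed true rates.
- All entered: 0.33 × 50 = 16.5 vs 0.11 × 50 = 5.5 cases, a difference of 22 points.
- Assume all VI nausea is judged related, and a share m of DE nausea is Grade 1 and judged unrelated. DE then records 11% × (1 − m).
- m = 0.5 gives 5.5% (2.75 cases) and a difference of 27.5 points, 25% larger.
- m = 1 gives 0% and a difference of 33 points, 50% larger.

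For a real effect, the direction on the difference scale depends on these shares. If all nausea were mild, none were entered in DE and a share r were entered in VI, the recorded difference would be 33r points. That exceeds 22 only if r is above 22/33, or two thirds. On the ratio scale the recorded contrast is inflated whenever the entered share is higher in VI than in DE.

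**The case against.** The strongest case on the other side has four parts.

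- **The exemption is a deliberate workload choice.** It drops only events that are both mild and judged unrelated. Mild events judged related to Vivitrol are kept, as is everything moderate or worse. This stands. The exemption is reasonable in itself; the difficulty comes from pairing it with a no-drug arm and unrestricted between-group testing.

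- **The protocol does not flatly contradict itself.** A reader might infer that section 11.22.1 requires what section 11.22.3 forbids. Section 11.22.1 in fact says events are handled under the specific instructions in that section and in Appendix A, and those two agree. What remains is narrow: the sentence putting all events on the AE Form does not match Appendix A, which uses that form for reportable events.

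- **Aim 1 does not set Vivitrol against DE.** A reader might infer that the study's main safety comparison is compromised, because Aim 1 lists adverse events and section 10.3 calls feasibility the primary focus. Aim 1 names VI and PNV, not DE. Its natural uses are events within those arms and VI against PNV, where both arms receive the drug and face the same causality question. The sentence in section 10.4.2 is also only permissive. This limits the concern to an optional comparison but does not remove it, since the plan allows that comparison without restriction.

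- **The large rejection rates depend on the test.** They come from an uncorrected chi-square with an empty control cell and small expected counts. Fisher's test cuts them sharply. In the nausea example, 16/50 vs 5/50 is already significant with full recording (p = 0.007; Fisher 0.013), so the exemption would distort a real difference, not create one. This stands.

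One counter-argument does not succeed. Causality is asked about the drug or the intervention, so a DE event could formally be judged related. Attributing a mild headache to an education session is implausible, however, so the imbalance remains.

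**Conclusion.** The concern holds within limits. As written, Grade 1 events need to be entered only if an unblinded clinician judges them related, and that will happen far less often in DE than in VI or PNV. A comparison of Grade 1 events between either Vivitrol arm and DE is therefore biased, with the tendency to show more mild events on Vivitrol.

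It would go too far to infer that adverse events cannot be compared between any arms. VI versus PNV is largely unaffected. Comparisons of Grade 2 or above and of serious events are unaffected, as is the primary outcome.

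No firm size can be given. The rejection rates of 1.8% to 75% (chi-square) or about 0% to 38% (Fisher) rest on an assumed 20% background rate, assumed attribution of 10% to 50% in VI and none in DE. At the low end the effect disappears. They show that the problem could matter, not that it will. It is worth correcting because the correction costs almost nothing.

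**What to change.** Preferred: add to section 10.4.2 that adverse event comparisons with DE are restricted to Grade 2 or above and serious events, and that Grade 1 events are reported descriptively within VI and PNV. This is one sentence with no change to data collection. The cost is that mild events cannot be compared with DE.

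Alternative: enter events of every grade in all three arms regardless of relationship. The adverse event question is already asked at visits, so the cost is more form entries of low information value.

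In either case, align the AE Form sentence in section 11.22.1 with section 11.22.3 and Appendix A, so that sites have one rule for which events go on the form and into the data system.

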11.23 Possible Risks of Study Medications

The most serious adverse effect of naltrexone is hepatocellular injury, which has almost always been associated with oral doses of 1400 to 2100 mg per week. Recent study findings show that no evidence of liver toxicity was found in those receiving monthly Vivitrol[®] injections such as provided in this study. Participants will not be allowed to participate if there is any indication or report of acute symptomatic hepatitis or liver failure.

Vivitrol[®] injections may be followed by pain, tenderness, induration, swelling, redness, bruising, or itching. Injection site reactions have been the most common adverse events associated with Vivitrol[®], but the injection site will be monitored after each injections. Any participant exhibiting adverse events will be evaluated by the study physician for possible referral to a surgeon if warranted. Other side effects may include nausea and vomiting. Continued use of naltrexone is not associated with tolerance or addiction, but naltrexone will precipitate withdrawal if given to a person who is physiologically dependent on opioids. To eliminate this risk, a naloxone challenge will be administered to each participant in this condition before administration of each Vivitrol injection.

12.0 DATA MANAGEMENT AND PROCEDURES

This protocol will utilize the UCLA ISAP Data Management Center (DMC). A web-based distributed data entry model will be implemented. This electronic data capture (EDC) system will be developed to ensure that guidelines and regulations surrounding the use of computerized systems used in clinical trials are upheld.

12.1 Operations Manual

An Operations Manual or Standard Operating Procedure documents will be provided for this study that incorporates procedures from this protocol with those procedures in more detail as necessary for the day-to-day conduct of the trial. The Operations Manual will be used to train study staff, to provide reference for study procedures, and to support quality management activities.

12.2 Data and Statistics Center Responsibilities

The DMC will 1) develop and apply data management procedures to ensure the collection of accurate and good-quality data, 2) provide source documents and electronic Case Report Forms (eCRFs) for the collection of all data required by the study, 3) develop data dictionaries for each eCRF that will comprehensively define each data element, 4) prepare instructions for the use of EDC system and for the completion of eCRFs, 5) perform data cleaning activities prior to any interim analyses and prior to the final study database lock.

12.3 Data Collection and Entry

Data will be collected on source documents and entered by the site into eCRFs or in the EDC, or will be collected via direct entry into the eCRF. In the event that the EDC is not available, the DMC will provide paper source documents and completion instructions. Data will be entered into the EDC in accordance with the instructions provided during project-specific training and guidelines established by the DMC. Data entry into the eCRFs shall be performed by authorized individuals. Selected eCRFs may also require the investigator's electronic signature.

The investigator is responsible for maintaining accurate, complete and up-to-date research records. In addition, the investigator is responsible for ensuring the timely completion of eCRFs for each research participant.

